10.1.3.2 Cohort Expansion in Part 2C

Part 2C will be an expansion phase of the BMS-986207 in combination with nivolumab and ipilimumab in participants with advanced treatment-naïve NSCLC whose tumor cells express $\geq 1\%$ PD-L1.

The sample size for Part 2C is based on assessing an initial [REDACTED] activity signal as estimated by the ORR following treatment in the triplet combination arm and to provide additional information for the safety profile in the 1L NSCLC population.

One or two doses are planned to be evaluated in Part 2C and a minimum of 20 participants are enrolled per dose level of BMS-986207. So approximately 40 evaluable participants in total with 1L NSCLC with tumor cell PD-L1 expression of $\geq 1\%$ will be treated with BMS-986207 in combination with nivolumab and ipilimumab.

In the event pre-existing PD-L1 results are not confirmed by the central lab test, additional participants (up to 20%) will be enrolled to achieve a sample size of 40 evaluable participants.

The following Bayesian posterior probability (PP) criteria will be used to assess signal of anti-tumor activity with benchmark of 36% as unfavorable ORR and 56% as desirable ORR:^{44,45}

- An [REDACTED] activity signal is based on ORR satisfying the dual criteria: PP (ORR ≥ 0.56) $\geq 40\%$ and PP (ORR ≥ 0.36) $\geq 80\%$
- A lack of activity signal is based on ORR meeting the criterion: PP (ORR ≥ 0.36) $< 20\%$

A beta prior distribution beta (1, 1) for ORR and Binomial Bin (n, ORR) likelihood for number of responders were used.

Based on the above criteria, for each dose level a total of 20 evaluable participants in Part 2C will provide approximately 6.5% chance to show [REDACTED] activity when a true ORR is 36%, and at least 63% chance of showing activity signal if the true ORR is 56% or more (see [Table 10.1.3.2-1](#))

The ORR thresholds for efficacy signal (responders $\geq 11/20$) and lack of efficacy ($\leq 6/20$) and the operating characteristics of the posterior probability criteria are shown in [Table 10.1.3.2-1](#).

Table 10.1.3.2-1: Operating characteristics of criteria for antitumor activity by ORR

Sample Size	True ORR	PP (Activity)	PP (No Activity)	PP (Inconclusive)	Responder Cutoff Activity/ No Activity
20	0.3	0.017	0.416	0.566	11/6
20	0.36	0.065	0.217	0.718	11/6
20	0.5	0.412	0.021	0.567	11/6
20	0.56	0.626	0.005	0.369	11/6
20	0.6	0.755	0.002	0.243	11/6
22	0.3	0.014	0.313	0.673	12/6
22	0.36	0.058	0.14	0.801	12/6
22	0.5	0.416	0.008	0.576	12/6
22	0.56	0.64	0.002	0.358	12/6
22	0.6	0.772	0	0.228	12/6
24	0.3	0.012	0.389	0.6	13/7
24	0.36	0.053	0.182	0.765	13/7
24	0.5	0.419	0.011	0.569	13/7
24	0.56	0.653	0.002	0.345	13/7
24	0.6	0.787	0.001	0.212	13/7
26	0.3	0.009	0.46	0.53	14/8
26	0.36	0.048	0.226	0.726	14/8
26	0.5	0.423	0.014	0.563	14/8
26	0.56	0.664	0.003	0.333	14/8
26	0.6	0.801	0.001	0.199	14/8

ORR, objective response rate; PP: posterior probability

In addition, to the above, [Table 10.1.3.2-2](#) summarizes the 80% exact CI for various ORRs for combination therapy with sample sizes of 20, 22, 24, and 26. For example, 11 responders will need to be observed in 20 evaluable participants respectively, (an observed ORR \geq 55%) for the lower bound of the 80% CI to exclude a 36% ORR.

Table 10.1.3.2-2: Potential ORR in 1L NSCLC ($\geq 1\%$ PD-L1) and Exact 80% CI

Sample size	Number of Responders	ORR	80% Exact CI
20	10	0.5	[0.34, 0.66]
	11	0.55	[0.38, 0.71]
	13	0.65	[0.48, 0.79]
	14	0.7	[0.53, 0.83]
22	11	0.5	[0.35, 0.65]
	12	0.55	[0.39, 0.70]
	14	0.64	[0.48, 0.78]
	16	0.73	[0.57, 0.85]
24	12	0.5	[0.35, 0.65]
	13	0.54	[0.39, 0.69]
	15	0.63	[0.47, 0.75]
	17	0.71	[0.56, 0.83]
26	13	0.5	[0.36, 0.64]
	14	0.54	[0.40, 0.68]
	16	0.62	[0.47, 0.75]
	18	0.69	[0.55, 0.81]

Abbreviations: 1L NSCLC, first-line non-small cell lung cancer; CI, confidence interval; ORR, objective response rate; PD-L1, programmed cell death ligand 1.

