10.3.1 Efficacy Analyses

The primary efficacy analyses (Table 10.3.1-1) will be performed on the treated population for the final analysis. Efficacy analyses based on the response-evaluable population may be performed for interim analyses when the minimum follow-up period is less than sufficient to warrant adequate interpretation of the result. Details of the censoring scheme on time-to-event endpoints such as DOR, PFS, [REDACTED] will be described in the Statistical Analysis Plan.

Table 10.3.1-1: Efficacy - Statistical Analyses

Endpoint	Statistical Analysis Methods
ORR is defined as the proportion of all treated participants whose BOR is either CR or PR by Investigator per RECIST v1.1 BOR for a participant will be assessed per RECIST v1.1 by Investigator	Estimate of ORR and corresponding 2-sided exact 95% CI using the Clopper-Pearson method by treatment for each tumor type (Parts 2A and 2B). Estimate of ORR and corresponding 2-sided exact 80% CI using the Clopper-Pearson method by treatment for 1L NSCLC with PD-L1 expression $\geq 1\%$ by central lab (Part 2C).
Median DOR DOR for a participant with a BOR of CR or PR is defined as the time between the date of first response and the date of the first objectively documented tumor progression per RECIST v1.1 or death, whichever occurs first.	Median duration of response using the Kaplan-Meier method and corresponding 2-sided 95% CI using Brookmeyer and Crowley methodology (using log-log transformation) by treatment for each tumor type and treatment (Parts 1A, 2B, and 2C)
PFSR at 24 weeks PFS for a participant is defined as the time from the first dosing date (Part 1, Part 2A, and Part 2B)/randomization date (Part 2C) to the date of first objectively documented disease progression or death due to any cause, whichever occurs first.	Estimate by the Kaplan-Meier method and corresponding 95% CI will be derived based on Greenwood formula by treatment for each tumor type.

Abbreviations: BOR, best overall response; CI, confidence interval; CR, complete response; DOR, duration of response; ORR, overall response rate; PFS, progression free survival; PFSR, progression free survival rate; PR partial response; RECIST, Response Evaluation Criteria In Solid Tumors

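### Part 2C: the printed lack-of-efficacy threshold of ≤6/20 does not meet the plan's own posterior criterion; the largest count that does is 5/20

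*Combined protocol and SAP*

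**What the plan says.** Section 10.1.3.2 says that Bayesian posterior probability "criteria will be used to assess signal of anti-tumor activity with benchmark of" 36% (unfavourable ORR) and 56% (desirable ORR). There are two rules:

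- Activity needs both PP(ORR ≥ 0.56) ≥ 40% and PP(ORR ≥ 0.36) ≥ 80%.
- For the other direction, "A lack of activity signal is based on ORR meeting the criterion" PP(ORR ≥ 0.36) < 20%.

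The model is stated in full: "A beta prior distribution beta (1, 1) for ORR and Binomial Bin (n, ORR) likelihood for number of responders were used". The rules are applied to each dose level at 20 evaluable participants.

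The section then turns the rules into counts at n = 20. The efficacy signal is 11 or more responders. The other threshold reads "lack of efficacy ($\leq 6/20$) and the operating characteristics of the posterior probability criteria are shown in" Table 10.1.3.2-1. In that table the last column, headed "Responder Cutoff Activity/ No Activity", shows 11/6, 12/6, 13/7 and 14/8 for n = 20, 22, 24 and 26, with no inequality signs.

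**The concern.** The section states one decision rule in two ways, as a posterior probability and as a responder count, and the two disagree at exactly 6/20. A reader who applies the count reports lack of activity; a reader who applies the criterion reports an inconclusive result. The operating characteristics that the sentence points to would also not describe the count that it prints.

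ORR is a primary endpoint of Part 2C (Table 4-1). Twenty is the minimum enrolment per dose level (Section 5.1.2.7) and the size used for the per-dose calculation, so the n = 20 count is the one most likely to be lifted into a report or a dose discussion.

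**Working it through.** **Inputs** (all from Section 10.1.3.2): Beta(1,1) prior; binomial likelihood; lack of activity if PP(ORR ≥ 0.36) < 0.20; activity if PP(ORR ≥ 0.56) ≥ 0.40 and PP(ORR ≥ 0.36) ≥ 0.80; n = 20; printed thresholds ≥11/20 and ≤6/20; the rows of Table 10.1.3.2-1.

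**Step 1. Posterior.** With r responders out of n, ORR has a Beta(1 + r, 1 + n − r) posterior. For this prior, PP(ORR ≥ p) equals the probability that a Binomial(n + 1, p) count is at most r, which gives a second way to check each value.

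**Step 2. Reproduce the activity cutoff.** At 11/20, PP(ORR ≥ 0.56) = 0.451 and PP(ORR ≥ 0.36) = 0.961, so both conditions hold. At 10/20, PP(ORR ≥ 0.56) = 0.288 and the first fails. The printed ≥11/20 is right.

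**Step 3. Lack-of-activity cutoff at n = 20.**

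| Responders | Posterior | PP(ORR ≥ 0.36) | Below 0.20? |
|---|---|---|---|
| 4 | Beta(5,17) | 0.078 | yes |
| 5 | Beta(6,16) | 0.175 | yes |
| 6 | Beta(7,15) | 0.322 | no |

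At 6/20, PP(ORR ≥ 0.56) is 0.010, so activity fails as well and the result is inconclusive. No posterior value lies near 0.20, so reading the criterion as < or ≤ makes no difference. Nor does the prior rescue the printed count: under Beta(0.5,0.5), Beta(0.36,0.64), Beta(0.56,0.44) and a near-zero Beta(0.001,0.001), PP(ORR ≥ 0.36) at 6/20 runs from 0.266 to 0.304.

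**Step 4. Which count does the table use?** With X ~ Binomial(20, true ORR) and inconclusive = 1 − P(X ≥ 11) − P(no activity):

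| True ORR | Table: no activity | P(X ≤ 5) | P(X ≤ 6) | P(X = 6) | Table: inconclusive | Inconclusive with ≤5 | Inconclusive with ≤6 |
|---|---|---|---|---|---|---|---|
| 0.30 | 0.416 | 0.416 | 0.608 | 0.192 | 0.566 | 0.566 | 0.375 |
| 0.36 | 0.217 | 0.217 | 0.380 | 0.163 | 0.718 | 0.718 | 0.555 |
| 0.50 | 0.021 | 0.021 | 0.058 | 0.037 | 0.567 | 0.567 | 0.530 |
| 0.56 | 0.005 | 0.005 | 0.017 | 0.012 | 0.369 | 0.369 | 0.356 |
| 0.60 | 0.002 | 0.002 | 0.006 | 0.005 | 0.243 | 0.243 | 0.238 |

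The table follows the ≤5/20 rule in every n = 20 row.

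**Step 5. The other sample sizes.** Values are PP(ORR ≥ 0.36).

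| n | Cutoff shown | At the cutoff | One fewer |
|---|---|---|---|
| 22 | 6 | 0.223 (fails) | 5/22: 0.111 (meets) |
| 24 | 7 | 0.271 (fails) | 6/24: 0.148 (meets) |
| 26 | 8 | 0.318 (fails) | 7/26: 0.188 (meets) |

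The no-activity column equals P(X ≤ cutoff − 1) in all 20 rows. For example, at true ORR 0.30, 0.36 and 0.50 it is 0.313, 0.140 and 0.008 for n = 22, and 0.460, 0.226 and 0.014 for n = 26. The second figure in the cutoff column is therefore a strict upper bound throughout.

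**The case against.** The arithmetic is hard to dispute, so the case against concerns how much it matters.

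- **The posterior criterion governs.** It is stated correctly and completely, and the sentence with the count only describes it. That is fair, and it is why criterion and table should stand. It does not make the printed count harmless, because the count is the form most people will apply.
- **The count applies only when a dose level has exactly 20 evaluable participants.** Correct. With another number the posterior has to be computed, or another row used. But 20 is the size on which the section bases its per-dose calculation.
- **Little turns on the label.** Section 3.1 says that no prospective hypotheses are formally evaluated, and Section 10.3.8 plans no formal inference needing a significance adjustment. An observed 6/20 is an ORR of 30%, below the 36% benchmark, and is not an activity signal on either reading. This stands and limits the consequence.
- **The point rests on one inequality sign.** A strict < in the typeset protocol would agree with the criterion and the table, so the sign is worth a glance there. Nothing shows that it was altered, and the strict sign in the 20% criterion of the same section is intact.
- **The column label is not an error.** Agreed. Adding signs to it is a clarification that guards against the same misreading at n = 22, 24 and 26.

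**Conclusion.** The concern holds. Under the plan's own prior and criterion, lack of activity at n = 20 means 5 or fewer responders, and 6/20 is inconclusive. The ≤ in the text is the one false statement; the table's probabilities are correct.

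Applying the text literally would move only results of exactly 6/20. The chance of a no-activity call would rise by 19 percentage points at a true ORR of 30% and by 16 points at 36%, but by only 3.7 points at 50% and 1.2 points at 56%. The large shifts thus sit at or below the unfavourable benchmark. Because the plan ties no binding stopping or dose-dropping rule to this signal, the consequence is a mislabelled signal on a primary endpoint.

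The ≥11/20 cutoff, the 6.5% and 63% in the sample-size text, and the planned analysis ("Estimate of ORR and corresponding 2-sided exact 80% CI using the Clopper-Pearson method") do not change. The conclusion assumes 20 evaluable participants at the dose level and the stated Beta(1,1) prior; the other priors tried give the same classification of 6/20. It should be corrected, although it does not affect the design.

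**What to change.** In the text of Section 10.1.3.2, replace ≤6/20 with ≤5/20 (equivalently <6/20). In Table 10.1.3.2-1, head the last column so that it reads ≥ for activity and < for no activity; no activity then applies at ≤5/20, ≤5/22, ≤6/24 and ≤7/26. Leave the tabulated probabilities as they are. Use the same inequality in the SAP, which Section 10.3 says will be finalised before database lock.

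The cost is one number in one sentence and one column label, with no change to the design or sample size.

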10.2 Populations for Analyses

For purposes of analysis, the populations in are defined in Table 10.2-1.

Table 10.2-1: Population for Analyses

Population	Description
Enrolled	All participants who sign informed consent and are registered into the IRT
NSCLC efficacy	All treated participants in Part 2C with PD-L1 $\geq 1\%$ by central lab
Treated	All participants who take at least 1 dose of study treatment.
Response-evaluable	All treated participants with measurable disease at baseline and one of the following: (a) at least 1 post baseline tumor assessment, (b) clinical progression, (c) death
Pharmacokinetic	All treated participants who have evaluable concentration-time data
Immunogenicity	All treated participants who have baseline and at least 1 post baseline pre-infusion immunogenicity assessment

Abbreviations: IRT, Interactive Response Technology.

10.3 Statistical Analyses

The statistical analysis plan will be developed and finalized before database lock, and below is a summary of planned statistical analyses of the primary and secondary endpoints.

10.3.1 Efficacy Analyses

The primary efficacy analyses (Table 10.3.1-1) will be performed on the treated population for the final analysis. Efficacy analyses based on the response-evaluable population may be performed for interim analyses when the minimum follow-up period is less than sufficient to warrant adequate interpretation of the result. Details of the censoring scheme on time-to-event endpoints such as DOR, PFS, [REDACTED] will be described in the Statistical Analysis Plan.

Table 10.3.1-1: Efficacy - Statistical Analyses

Endpoint	Statistical Analysis Methods
ORR is defined as the proportion of all treated participants whose BOR is either CR or PR by Investigator per RECIST v1.1 BOR for a participant will be assessed per RECIST v1.1 by Investigator	Estimate of ORR and corresponding 2-sided exact 95% CI using the Clopper-Pearson method by treatment for each tumor type (Parts 2A and 2B). Estimate of ORR and corresponding 2-sided exact 80% CI using the Clopper-Pearson method by treatment for 1L NSCLC with PD-L1 expression $\geq 1\%$ by central lab (Part 2C).
Median DOR DOR for a participant with a BOR of CR or PR is defined as the time between the date of first response and the date of the first objectively documented tumor progression per RECIST v1.1 or death, whichever occurs first.	Median duration of response using the Kaplan-Meier method and corresponding 2-sided 95% CI using Brookmeyer and Crowley methodology (using log-log transformation) by treatment for each tumor type and treatment (Parts 1A, 2B, and 2C)
PFSR at 24 weeks PFS for a participant is defined as the time from the first dosing date (Part 1, Part 2A, and Part 2B)/randomization date (Part 2C) to the date of first objectively documented disease progression or death due to any cause, whichever occurs first.	Estimate by the Kaplan-Meier method and corresponding 95% CI will be derived based on Greenwood formula by treatment for each tumor type.

Abbreviations: BOR, best overall response; CI, confidence interval; CR, complete response; DOR, duration of response; ORR, overall response rate; PFS, progression free survival; PFSR, progression free survival rate; PR partial response; RECIST, Response Evaluation Criteria In Solid Tumors

10.3.2 Safety Analyses

All safety analyses will be performed on the treated population.

Endpoint	Statistical Analysis Methods
Incidence of DLTs, AEs, SAEs, AEs leading to discontinuation, and death AEs will be graded according to CTCAE v4.03	DLT rate by dose level, frequency distribution of treated participants with AE using the worst CTC grade. Participants will only be counted (1) once at the PT level, (2) once at the system organ class level, and (3) once in the 'total participant' row at their worst CTC grade, regardless of system organ class or PT.
Laboratory abnormalities Laboratory values will be graded according to CTCAE v4.03.	Laboratory shift table using the worst CTC grade on treatment per participant

Abbreviations: AE, adverse event; CTC, common terminology criteria; CTCAE, common terminology criteria for adverse events; DLTs, dose-limiting toxicities; PT, preferred term; SAE, serious adverse event.

In addition, continuous safety monitoring for toxicity will be conducted in the NSCLC Expansion Phase 2C as described in [Section 10.3.8](#).

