Recently, reports in the literature have shown comparable efficacy results with anti-TIGIT agents in combination with anti-PD-(L)1 agents, pembrolizumab and atezolizumab, in most tumor types.^{15,16} Best responses, however, were observed in those studies in 1L and previously treated NSCLC participants whose tumors expressed PD-L1. A randomized Phase 2 study comparing the anti-TIGIT agent tiragolumab plus atezolizumab versus placebo plus atezolizumab in PD-L1-positive 1L Stage IV NSCLC patients demonstrated improvement in the overall response rate (ORR; 37% vs. 21% with atezolizumab alone). The treatment regimen was well tolerated, with safety similar to that seen in the placebo plus atezolizumab treatment (see [Section 5.4.4](#) for more details).¹⁶ In addition, recent data presented from a Phase 1 study (NCT02964013) of the anti-TIGIT antibody vibostolimab plus pembrolizumab in participants with anti-PD-(L)1-naive NSCLC demonstrated anti-tumor activity (ORR 29% and 46% in patients with PDL1-positive disease).¹⁷ These data suggest that combining anti-TIGIT with anti-PD-(L)1 can be safe, tolerable, and have clinical benefits in PD-L1-positive 1L NSCLC patients.¹⁷

As of 20-Oct-2021, the safety profile of BMS-986207 1200 mg Q3W in combination with nivolumab 360 mg Q3W and ipilimumab 1 mg/kg Q6W has been evaluated in 6 subjects with multiple metastatic solid tumors in CA020002 Part 1C. Of the 4 dose-limiting toxicity (DLT)-evaluable participants, 2 participants reported DLTs (Grade 3 encephalitis and Grade 3 bullous dermatitis [n = 1 each]). Per Bayesian optimal interval (BOIN) design, in all the remaining and future subjects, BMS-986207 was de-escalated to a lower dose (600 mg Q3W). For details, see [Section 3.2.1.4](#).

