^b Participants were enrolled at a single site under site-specific Amendments 6, 7, and 8. This substudy has been closed for enrollment.

^c The safety profile of BMS-986207 1200 mg Q3W combined with nivolumab 360 mg Q3W and ipilimumab 1 mg/kg Q6W has been evaluated in 6 subjects. Of these subjects, 4 were DLT evaluable, and 2 developed DLTs. Per BOIN design, in all the remaining and future subjects in Part 1C, BMS-986207 was de-escalated to 600 mg Q3W (for details, see [Section 3.2.1.4](#)). Planned dose levels for BMS-986207 may be further modified based on generated data and additional doses, including 360 mg Q3W, may be assessed per BOIN design and for dose optimization analysis at sponsor discretion and based upon discussion and agreement with investigators.

^d Part 2C will enroll a minimum of 20 participants per dose level of BMS-986207. One or two doses are planned to be evaluated and selected from the range of doses assessed as tolerable and not exceeding the maximum tolerated dose in Part 1C. If two doses will be tested at the sponsor's discretion, participants will be randomized in a 1:2 ratio schema between the highest dose selected in Part 1C and the next lower dose, after at least 10 participants will have been tested at the dose found safe in Part 1C.

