If 3 or 4 DLTs are observed out of 12 DLT evaluable participants as shown in [Table 5.1.2.6-1](#), the design recommends to stay at the same dose level, indicating that more participants may need to be evaluated to determine whether the dose level is safe. After considering additional information such as provided in [Table 5.1.2.6-2](#) and the totality of available data including safety, PK/pharmacodynamics from all treated participants, a lower dose may be considered for evaluation, (eg, if 4 /12 DLTs) or the dose may be considered safe (eg, with 3/12 DLTs) based on discussion between the Investigator and Sponsor/Medical Monitor, and based on posterior probability of the DLT rate exceeding the target. Once a dose is declared safe based on at least 6 participants, an additional 6-12 participants may be treated up to a total of 18 to continue to confirm the safety of the selected dose. At the same time, enrollment in Part 2C may begin. In addition, another cohort up to 18 participants may be treated at the next lower dose of BMS-986207 to optimize dose selection. Participants who do not complete the DLT observation period for

reasons other than DLTs may be replaced. De-escalation may be considered if the safety and tolerability profile for the selected BMS-986207 dose is evaluated as not acceptable, after discussion between the Investigator(s) and the Sponsor/Medical Monitor.

Table 5.1.2.6-1: Triplet Safety Evaluation Guidance for DLT-Related Decisions by BOIN Design Framework

Actions based on number of DLT's	The number of DLT-evaluable participants treated at the current dose									
	3	4	5	6	7	8	9	10	11	12
Declare dose tolerable if # of DLT \leq^a	0/NA	0/NA	1/NA	1	1	1	2	2	2	2
Stay if # of DLT =	1	1	NA	2	2	2	3	3	3	3,4
De-escalate if # of DLT \geq	2	2	2	3	3	3	4	4	4	5
Eliminate if # of DLT \geq	3	3	4	4	5	5	5	6	6	7

Abbreviations: BOIN, Bayesian optimal interval; DLT, dose-limiting toxicity

^a The decision meets the same requirements as needed to “escalate” in standard design. NA indicates that decisions to declare a dose tolerable will not be made with fewer than 6 participants

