5 BOIN ESCALATION DESIGN SIMULATION WITH 2 DOSE LEVELS, PART 1C

The Bayesian optimal interval (BOIN) design framework will be used to guide the safety evaluation of BMS-986207 in combination with nivolumab and ipilimumab in Part 1C. The design is typically also used to determine maximum tolerated dose (MTD) selection in cases where more doses are evaluated.^{5,6}

As a single dose level of BMS-986207 will be evaluated in this triplet combination (with potential for a de-escalation if needed), the goal in this study part is to assess if the dose is tolerable. Therefore MTD reference below (as in typical multi-dose level design) represents a ‘tolerable

dose' in Part 1C. As an escalation decision is not of interest in Part 1C, a design recommendation to declare a dose as tolerable is based on meeting the same criteria needed to escalate.

The target toxicity rate for the MTD is $\phi = 0.3$ and the maximum sample size is 12. Participants will be enrolled in cohorts of 3. The BOIN design framework uses the following rule optimized to minimize the probability of incorrect dose assignment, to guide dose escalation/de-escalation:

- If the observed DLT rate at the current dose is ≤ 0.236 , declare the dose tolerable;
- If it is ≥ 0.359 , de-escalate the dose to the next lower dose level;
- Otherwise, stay at the current dose.

The design MTD selection approach described next, is included for general information on the design; however, it is not used in this study. After the trial is completed, selection of the MTD is based on isotonic regression as specified in Liu and Yuan (2015).⁵ Specifically, the MTD is the dose for which the isotonic estimate of the DLT rate is closest to the target DLT rate. If there are ties, select the higher dose level when the isotonic estimate is lower than the target DLT rate and select the lower dose level when the isotonic estimate is greater than or equal to the target DLT rate.

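### The Part 1 DLT rate by dose is to be reported on all treated participants, while Part 1 dose-finding counts DLT-evaluable participants (33% against 50% at 1200 mg in Part 1C)

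*Combined protocol and SAP*

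**What the plan says.** Section 10.3.2 opens with "All safety analyses will be performed on the treated population". The first analysis listed under it is "DLT rate by dose level, frequency distribution of treated participants with AE using the worst CTC grade". No separate denominator is given for the DLT rate, and no time window for its numerator. Section 10.2, Table 10.2-1, defines the treated population as "All participants who take at least 1 dose of study treatment" and has no row for DLT-evaluable participants.

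Part 1 dose-finding uses a different unit:

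- **Part 1C.** The columns of the decision table in Section 5.1.2.6 (Table 5.1.2.6-1) are headed "The number of DLT-evaluable participants treated at the current dose", and at least 6 such participants are needed before a dose can be called tolerable.
- **Parts 1A and 1B.** Section 10.1.1 sets the minimum at the MTD (6) and the maximum per dose (12) in DLT-evaluable participants, and the model uses information from the DLT period only.
- **All of Part 1.** Participants who leave the DLT period for reasons other than a DLT may be replaced (Sections 5.1.2.5, 5.1.2.6 and 7.4.1).

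Table 4-1 makes the incidence of AEs meeting DLT criteria part of the primary endpoint for Parts 1A, 1B and 1C, and also for 2A and 2B.

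**The concern.** A treated participant who leaves the DLT period early without a DLT has not been observed long enough to count as DLT-free. The design recognises this by leaving such participants out of its counts and allowing replacement. Section 10.3.2, followed as written, puts them back into the denominator as if they had completed the period without a DLT, and each replacement enlarges the denominator again.

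The reported DLT rate at a dose would then differ from the rate behind the decision taken at that dose. The gap would vary between doses with the share of non-evaluable participants, which makes rates harder to compare across doses or against the 30% target of Part 1C.

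**Working it through.** **Inputs**

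- Treated at 1200 mg in Part 1C: 6. Section 5.1.2.2, footnote to the treatment-cohort figure: "ipilimumab 1 mg/kg Q6W has been evaluated in 6 subjects".
- DLT-evaluable: 4, with DLT: 2. Same footnote: "Of these subjects, 4 were DLT evaluable, and 2 developed DLTs". Section 3.1 agrees: "Of the 4 dose-limiting toxicity (DLT)-evaluable participants, 2 participants reported DLTs".
- Decision boundaries: Appendix 12, Section 5, gives "If the observed DLT rate at the current dose is ≤ 0.236 , declare the dose tolerable" and a de-escalation boundary of 0.359.

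**Step 1: reproduce the plan's boundaries.** Take the target φ = 0.30. The two reference rates are not stated in the plan, so I assume φ1 = 0.6φ = 0.18 and φ2 = 1.4φ = 0.42.

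- Lower boundary: log[(1 − φ1)/(1 − φ)] / log[φ(1 − φ1)/(φ1(1 − φ))] = log(0.82/0.70) / log(0.246/0.126) = 0.2365.
- Upper boundary: log[(1 − φ)/(1 − φ2)] / log[φ2(1 − φ)/(φ(1 − φ2))] = log(0.70/0.58) / log(0.294/0.174) = 0.3585.

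These match the stated 0.236 and 0.359. All the tolerable, stay, de-escalate and eliminate entries of Table 5.1.2.6-1 for n = 3 to 12 also reproduce (elimination when the posterior probability of a rate above 0.30 exceeds 0.95 under a Beta(1,1) prior). The design is internally sound on its own denominator.

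**Step 2: general relation.** Let T be the number treated, E the number DLT-evaluable (E ≤ T) and D the number with a DLT inside the DLT period. Anyone with such a DLT is evaluable, so D is the same under both denominators:

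D/T = (D/E) × (E/T) = (D/E) × (1 − f), where f = (T − E)/T.

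For in-period DLTs the treated rate can therefore never exceed the evaluable rate. It equals it only if f = 0 or D = 0.

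**Step 3: the 1200 mg dose.**

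| Denominator | Rate | Exact 95% CI |
|---|---|---|
| DLT-evaluable | 2/4 = 50.0% | 6.8% to 93.2% |
| Treated | 2/6 = 33.3% | 4.3% to 77.7% |

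Here f = 2/6 = 1/3, and 50.0% × 2/3 = 33.3%. The difference is 16.7 percentage points. Against the boundaries, 0.500 is above 0.359, which is the de-escalation that was made; 0.333 lies between 0.236 and 0.359. Table 5.1.2.6-1 shows the same contrast: 2 DLTs in 4 evaluable participants is de-escalate, 2 in 6 is stay.

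**Step 4: what happens if later events are counted.** Section 10.3.2 does not confine the numerator to the DLT period, and Section 7.4.1 recognises DLTs that occur after it. As a hypothetical, one additional participant with a late event would give 3/6 = 50%, and two would give 4/6 = 67%. The direction found in Step 2 therefore depends on the window.

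**The case against.** Several points against a strong version of this concern are right.

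- **Not every DLT rule uses DLT-evaluable participants.** A reader might infer that it does. Section 5.1.2.7 applies the 33% rule to all participants treated in Parts 2A or 2B, and Section 10.3.8 counts every treated Part 2C participant as evaluable. The mismatch is confined to Part 1.
- **The rate is not biased low without qualification.** As Step 4 shows, that holds only for DLTs counted within the DLT period, which Section 10.3.2 does not specify.
- **Dose decisions do not pass through this summary.** Part 1C uses the decision table on DLT-evaluable counts; Parts 1A and 1B use the model on DLT-period data plus clinical assessment. It is tempting to say that 33% would undermine the 1200 mg de-escalation or distort the RP2D. The documents do not support that: the decision table is never applied to treated counts, and no section feeds the Section 10.3.2 rate into the RP2D.
- **The 1200 mg figures are preliminary (20-Oct-2021).** The text available for this review does not say why two participants were not evaluable, so the example does not show an effect of dropout.
- **Precision is poor.** The two confidence intervals overlap almost entirely, and Section 3.1 says that no hypothesis is formally evaluated.

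It can also be argued that the treated denominator comes from a general sentence, and that Section 10.3 is only a summary ahead of a SAP still to be finalised. This carries less weight. The sentence covers all safety analyses, the DLT rate is the first one listed beneath it, and no exception is made. A SAP that follows the protocol would inherit the denominator. Wide intervals do not make it the right one.

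**Conclusion.** The concern holds for the reported Part 1 DLT rate. The plan assigns that rate to the treated population and defines no DLT-evaluable set, although Part 1 dose-finding depends on one. For in-period DLTs the reported rate is multiplied by (1 − f); at 1200 mg this gives 33% in place of 50%.

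This rests on two assumptions: that the general sentence in Section 10.3.2 governs the DLT rate, and that the numerator is limited to the 28- or 42-day period. If later events are counted, the reported rate still need not match the decision rate, but the direction is no longer fixed.

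The issue is moderate. It concerns how a primary endpoint of Part 1 is reported; it changes no real-time dose decision and neither of the Part 2 toxicity rules.

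**What to change.** 1. **Table 10.2-1:** add a DLT-evaluable population, defined as treated participants in Parts 1A, 1B and 1C who either had a DLT in the DLT period or completed that period.
2. **Section 10.3.2:** compute the Part 1 DLT rate by dose level on that population, with the numerator limited to the DLT period (28 days in 1A and 1B, 42 days in 1C). Beside each rate show the number treated and the number not evaluable, with reasons.
3. **Section 10.3.2:** report AEs meeting DLT criteria outside the DLT period, and those in Part 2, separately on the treated population. Keep the treated population for all other safety summaries, and leave the Part 2 monitoring rules as they are.

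The cost is one table row and a few sentences in a SAP that is not yet final. The downside for the sponsor is that reported Part 1 DLT rates may be somewhat less favourable.
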